6.3 MEASURES TO MINIMIZE BIAS: RANDOMIZATION AND BLINDING

After informed consent is given, a randomized assignment will be made by the VCU Investigational Pharmacy in random batches of 2, 4, or 8 subjects. Eligibility forms confirming eligibility will be transmitted via the OnCore clinical trials software and verified by the VCU Investigational Pharmacy prior to randomization. Investigational Pharmacy at VCUHS will administer either Vitamin C therapy or placebo. The randomization will be stratified to one of the two study arms.

6.4 STUDY INTERVENTION COMPLIANCE

Adherence to the protocol will be assessed and verified using participant drug log, review of electronic medical records and review of the eCRF.

6.5 CONCOMITANT THERAPY

Any concomitant medications as part of standard of care (particularly glucose infusion, insulin, albumin, corticosteroids, N-acetylcysteine, and antibiotics) provided will be recorded.

6.5.1 RESCUE MEDICINE

Not applicable.

7 STUDY INTERVENTION DISCONTINUATION AND PARTICIPANT DISCONTINUATION/WITHDRAWAL

7.1 DISCONTINUATION OF STUDY INTERVENTION

If subjects do not tolerate the drug due to side effects such as nausea, vomiting, flushing, rash, headache, diarrhea, develops crytalluria on urinalysis, or QTc prolongation >50% baseline, we will reduce the subsequent doses by 50%. If the QTc is greater than 550 msec at any time, the drug will be discontinued.

Loss of indwelling venous/arterial catheter or peripheral intravenous access will also trigger the stopping of Vitamin C infusions but subjects will remain on study. Blood glucose monitoring will continue via the central laboratory for 36 hours after the last infusion via peripheral IV draws or peripheral sticks. Biomarker sampling via peripheral IV and/or peripheral stick is allowable as it occurs only 4 times throughout the study and likely only once (if at all) after the patient has been discharged from the unit and is without a central line.

The study drug will be discontinued if a patient develops a metabolic acidosis unexplained by other etiologies (lactic acidosis secondary to septic shock). Determination of the presence of metabolic acidosis will be made by the clinical care team. Study drug will also be discontinued if primary care team or surrogate decision maker request withdrawal. Data collection will continue on these patients following withdrawal of study drug.

Requests to unblind a patient's study treatment can be made to the study (investigational) pharmacist or clinical care team. Unblinding study treatment should occur only in the case of an emergency when knowledge of the study treatment is essential for subject care to treat a serious adverse event and prevent further harm or death.

If possible, a decision to unblind should be discussed with the Principal Investigator or a sub-Investigator prior to unblinding the study treatment.

If a blind is broken (either intentionally or unintentionally), the circumstances should be documented as to who, what, when, and why and all documentation shall be kept by the study pharmacist.

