 - PT control/reference level (assuming 12 seconds)
- Liver enzymes and function tests at hours 48, 96, 168
 - AST, ALT, total bilirubin, alkaline phosphatase, albumin
- MELD-Na Score at hours 48, 96, 168
 - INR, creatinine, bilirubin, sodium
- Documented tolerability at hours 24, 48, 96
 - Need for dose reduction, headache, dizziness, dry mouth, nausea, vomiting, flushing, rash, hypotension, treatment related adverse events
- Documented safety at hours 24, 48, 96
 - QTc Interval (EKG)
 - Crystalluria (Urinalysis with microscopy and pH testing)
- Serum Biomarkers
 - Procalcitonin, C-reactive protein, thrombomodulin, thromboelastography (TEG), Receptor for Advanced

Glycation End Products, Tissue Factor Pathway Inhibitor at study hours 0, 48, 96, 168 (When feasible)

- Ascorbate level at hour 0, 48, 96, 168 (When feasible)
- Need for escalation of support i.e. need for ventilator or pressor support when these are not needed at baseline
- ICU-free days at day 28
- All-cause mortality to day 28 and day 90
- Hospital-free days at day 90

Study Population: A total of 20 adult subjects with alcoholic hepatitis and suspected or documented sepsis will be enrolled in this study. All participants will be enrolled at the Virginia Commonwealth University Health System (VCUHS).

Phase: Phase II

[figure not shown]
Description of Sites/Facilities Enrolling Participants: Subjects will be recruited from the Emergency Department (ED), inpatient medicine unit admitted to the Digestive Health Service (DHS), and Intensive Care Units (ICU) at VCUHS.

[figure not shown]
Description of Study Intervention: Participants will be randomized to receive either intravenous Vitamin C (sterile L-ascorbic acid mixed in 5% dextrose in water) or placebo (5% dextrose in water). Active treatment will continue for 96 hours, discharge from study hospital, study withdrawal, or death, whichever comes first.

[figure not shown]
Study Duration: Years 1-4

[figure not shown]
Participant Duration: 90 days

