3 OBJECTIVES AND ENDPOINTS

| OBJECTIVES | ENDPOINTS | JUSTIFICATION FOR ENDPOINTS |
|---|--|---|
| Primary | | |
| Vitamin C infusion will significantly attenuate hepatic dysfunction as measured by the model for end stage liver disease (MELD) score | Change in MELD score at 96 hours as compared to baseline when compared to placebo. | MELD score is an independent positive predictor of mortality in patients with AH. |
| Secondary | | |

| OBJECTIVES | ENDPOINTS | JUSTIFICATION FOR ENDPOINTS |
|--|--|---|
| Vitamin C infusion will be safe and tolerable in patients with severe alcoholic hepatitis . | Documented side effects and serious adverse events at hours 24, 48, 96 when compared with hour zero in high dose ascorbic acid versus placebo. | AscA infusion may cause dry mouth, nausea, vomiting, dizziness, headache, flushing, rash, diarrhea. AscA can be excreted from kidney and lead to crystalluria, so will monitor urine pH via urinalysis. Will also monitor EKGs for QTc changes. |
| Secondary | | |
| Vitamin C infusion will attenuate biomarkers of inflammation (C-Reactive Protein, procalcitonin), vascular injury (Thrombomodulin, Angiopoietin-2), while inducing the onset of a fibrinolytic state (Tissue Factor Pathway Inhibitor) | Modulation of available biomarkers | Changes in these biomarkers may provide mechanistic insight into how vitamin C attenuates inflammation |
| Secondary | | |
| Vitamin C Infusion will improve clinical endpoints in this patient population . | 
Change in SOFA Score and Components at hours 48, 96, 168
 
Change in CLIF-SOFA scores and Components at hour 48, 96, 168 when compared to placebo
 
Change in MELD-Na, MDF, Lille scores at hour 48, 96, 168 when compared to placebo
 
Ascorbate level at hour 0, 48, 96, 168 (When feasible)
 
ICU-free days at day 28
 
All-cause mortality to day 28, 90
 
Hospital-free days at day 90
 | CLIF-SOFA, MDF, MELD, and Lille scores are associated with mortality in alcoholic hepatitis. Ascorbate levels are associated with mortality in sepsis patients in the ICU. AH patients have prolonged hospitalizations and are frequently in the ICU. |

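### For any baseline QTc of 367 msec or more, the QTc dose-halving rule in section 7.1 cannot act before the 550 msec stop

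*Combined protocol and SAP*

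**What the plan says.** Section 7.1 (Discontinuation of Study Intervention) lists reasons for halving later doses: several side effects, crystalluria, and a QTc criterion, "QTc prolongation >50% baseline, we will reduce the subsequent doses by 50" per cent. The next sentence sets the stop: "If the QTc is greater than 550 msec at any time, the drug will be discontinued". Together they describe a graded response, reduce first and then stop.

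QTc is also a named safety measure. The Synopsis (1.1) lists it under documented safety at hours 24, 48 and 96, and the table in section 3 adds "Will also monitor EKGs for QTc changes". Section 8.1 schedules a 12-lead EKG at Hour 0 and at hours 24, 48, 72 and 96. No other section gives a QTc threshold, and the exclusion criteria in 5.2 set no QTc limit at entry.

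**The concern.** A dose-reduction trigger is useful only if a patient can reach it before the stopping threshold. Here the reduction trigger scales with baseline and the stop is fixed, so above some baseline the reduction trigger lies beyond the stop. If that baseline is low relative to the patients enrolled, the reduce-then-stop scheme becomes stop-only for QTc.

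Two things are at stake. A patient with substantial QTc prolongation below 550 msec stays on full dose unless someone acts at their own discretion, and then goes straight from full dose to discontinuation. In addition, the Synopsis lists the need for dose reduction as a tolerability outcome; for the affected patients that outcome cannot register a QTc-triggered reduction under the stated threshold.

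**Working it through.** **Inputs.** From section 7.1: halve if QTc exceeds baseline by more than 50%, that is, QTc > 1.5 × B, where B is baseline QTc in msec; stop if QTc > 550. The documents give no baseline QTc values, so the baselines below are illustrative. There is no derived figure in the plan to reproduce on this point; the crossover follows from the two rules.

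**Crossover.** Halving without stopping requires 1.5 × B < QTc ≤ 550. Such a QTc exists only if 1.5 × B < 550, so B < 550/1.5 = 366.7 msec. In whole milliseconds, B = 366 gives a trigger of 549.0, leaving only 550 as a value that halves without stopping. B = 367 gives 550.5, and the window is empty.

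**Size of the window by baseline.**

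| Baseline (msec) | Halving trigger, 1.5 × B | Window before stop | Rise from baseline to 550 |
|---|---|---|---|
| 340 | 510 | 510 to 550 | 210 (61.8%) |
| 350 | 525 | 525 to 550 | 200 (57.1%) |
| 360 | 540 | 540 to 550 | 190 (52.8%) |
| 367 | 550.5 | none | 183 (49.9%) |
| 400 | 600 | none | 150 (37.5%) |
| 440 | 660 | none | 110 (25.0%) |
| 480 | 720 | none | 70 (14.6%) |

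As an example, a rise from 440 to 549 msec is 109 msec, or 109/440 = 24.8%. It is below the 50% trigger and below 550, so neither rule applies.

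**Share of patients affected (assumption-dependent).** If baselines are normal with mean m and standard deviation s, the share at or above 366.7 is Φ((m − 366.7)/s).

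| Assumed mean, SD (msec) | Share with no window |
|---|---|
| 400, 40 | 79.8% |
| 400, 30 | 86.7% |
| 400, 20 | 95.2% |
| 420, 30 | 96.2% |
| 440, 40 | 96.7% |
| 440, 30 | 99.3% |
| 460, 40 | 99.0% |
| 460, 20 | over 99.9% |

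Of 20 patients, the expected number keeping any window is about 4 at (400, 40), 0.15 at (440, 30) and essentially 0 at (460, 20).

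**The case against.** The two rules never give incompatible instructions. Where both are met, the stricter action applies, and the 550 msec stop works at every baseline. That is right: for these patients the halving rule is redundant, and what is lost is the intermediate step.

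The phrase about 50% of baseline may be a slip for 50 msec, in which case the overlap would begin only at a baseline of 500 msec. The documents do not settle this. If it is a slip, the text still needs correcting, in the same line and towards the same value.

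The practical effect may be small. QTc prolongation is not among the physical risks of ascorbic acid listed in 2.3.1, and the documents give no basis for estimating how many patients would have a rise in the range where halving should have applied. This stands. The range of 0 to 4 counts patients who keep a window, not patients expected to need it.

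Other safeguards remain: dose reduction for intolerance or crystalluria, daily EKG and adverse-event review through hour 96, DSMB review, and a route for the clinicians, since "Study drug will also be discontinued if primary care team or surrogate decision maker request withdrawal". QTc prolongation would therefore still be seen and reported. This limits the seriousness, but it does not make the stated rule work. QTc is the only item in the halving list with a numeric threshold, so relying on discretion means setting that threshold aside and risks uneven handling.

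**Conclusion.** The point holds. On the literal reading of section 7.1, for every baseline QTc of 367 msec or more, any value that meets the halving trigger already exceeds the stop, and below 367 msec only a narrow window remains. This crossover needs no assumption about the population. The share affected does: about 80% to over 99.9% under the assumed baselines.

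This is a rule that cannot operate as written for those patients, and it should be fixed. It does not touch the primary endpoint, the sample size or the primary analysis method, and it does not leave QTc prolongation unmonitored.

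**What to change.** First confirm whether a percentage or a number of milliseconds was meant. Then replace the QTc criterion in 7.1 with a trigger that falls before 550 msec, for example *QTc increase of more than 50 msec from the Hour 0 EKG*. This puts the trigger at 450, 490 and 530 msec for baselines of 400, 440 and 480, and keeps it below the stop for any baseline under 500 (B + 50 < 550). State that at a baseline of 500 msec or more only the stop applies, or set a separate rule. Keep the 550 msec stop. The value of 50 msec is a suggestion, not taken from the documents; the clinical leads and the DSMB should confirm the final figure.

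A smaller percentage is a weaker choice: a 25% trigger reaches 550 at a baseline of 550/1.25 = 440 msec, and a 20% trigger at 550/1.20 = 458 msec.

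The cost is a one-line amendment and an eCRF check. No new procedures are needed, because the EKGs are already scheduled. Counted from the first dose, dose 16 falls nominally at 15 × 6 = 90 hours, so in practice the hour 24, 48 and 72 EKGs are the ones that can change a dose. The downside is somewhat more QTc-driven reductions. They would occur in both arms because treatment is blinded, would feed into the dose-reduction tolerability outcome, and would lower exposure for any vitamin C patient whose dose is halved, in a trial with 10 patients per arm.

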7.2 PARTICIPANT DISCONTINUATION/WITHDRAWAL FROM THE STUDY

Participants are free to withdraw from participation in the study at any time upon request.

7.3 LOST TO FOLLOW-UP

A participant will be considered lost to follow-up if he or she fails to return for 2 scheduled visits and is unable to be contacted by the study site staff.

The following actions must be taken if a participant fails to return to the clinic for a required study visit:

- The site will attempt to contact the participant and reschedule the missed visit within 4-8 weeks and counsel the participant on the importance of maintaining the assigned visit schedule and ascertain if the participant wishes to and/or should continue in the study.
- Before a participant is deemed lost to follow-up, the investigator or designee will make every effort to regain contact with the participant (where possible, 3 telephone calls and, if necessary, a certified letter to the participant's last known mailing address or local equivalent methods). These contact attempts should be documented in the participant's medical record or study file.
- Should the participant continue to be unreachable, he or she will be considered to have withdrawn from the study with a primary reason of lost to follow-up.

8 STUDY ASSESSMENTS AND PROCEDURES

8.1 EFFICACY ASSESSMENTS

Screening

Subjects will be evaluated for entry into the study according to stated inclusion and exclusion criteria. Individuals who are identified during screening as not eligible for the study need not complete all screening procedures. The reason for ineligible status will be documented on the Screen Failure Log.

The following information will be obtained or performed to evaluate each subject's qualifications for participation in the study:

- Demographic information including gender, date of birth, race, ethnicity
- Medical and medication history over the past 30 days
- Alcohol consumption history
- Collection of blood for chemistry, hematology, coagulation, microbiology, in female patients, a pregnancy test (urine pregnancy test or blood human chorionic gonadotropin (hCG)
- Urinalysis and urine and/or drug/toxicology screening, including acetaminophen
- Physical examination including height and weight (body mass index will be calculated based on these variables), and vital signs (systolic and diastolic blood pressure, pulse rate, respiratory rate, body temperature), skin exam (jaundice yes/no, spider angiomas yes/no), abdominal exam (ascites yes/no, hepatosplenomegaly yes/no) neurological exam (Glasgow Coma Scale, West-Haven Hepatic Encephalopathy Scale, asterix yes/no)
- Review inclusion and exclusion criteria
- Signed, written informed consent

Assessments at Baseline (Hour 0):

- Collection of concomitant medications (if applicable); including corticosteroids, albumin, thiamine, antibiotics, and N-acetylcysteine use
- Collection of blood for hematology, coagulation, clinical chemistries
- Vital signs and abbreviated physical exam, including Glasgow Coma Scale and West-Haven Scale
- 12-Lead EKG

- Documentation of negative urine or serum drug screen, negative acetaminophen serum level, and negative urine or serum pregnancy testing for human chorionic gonadotropin (hCG) if female

Treatment Day 1 (Hour 24):

- Collection of concomitant medications (if applicable)
- Collection and monitoring of vital signs: blood pressure, temperature, heart rate, oxygen saturation
- Abbreviated physical exam
- Collection of blood for standard of care (SOC) hematology, coagulation, clinical chemistry, and biomarkers
- Document urine volume, urinalysis
- 12-Lead EKG
- AE review and reporting

Treatment Day 2 (Hour 48):

- Collection of concomitant medications (if applicable)
- Collection and monitoring of vital signs: blood pressure, temperature, heart rate, oxygen saturation
- Abbreviated physical exam
- Collection of blood for hematology, coagulation, clinical chemistry, biomarkers
- Document urine volume, urinalysis
- 12-Lead EKG
- AE review and reporting

Treatment Day 3 (Hour 72):

- Collection of concomitant medications (if applicable)
- Collection and monitoring of vital signs: blood pressure, temperature, heart rate, oxygen saturation
- Abbreviated physical exam
- Collection of blood for standard of care: hematology, coagulation, clinical chemistry
- Document urine volume
- 12-Lead EKG
- AE review and reporting

Treatment Day 4 (Hour 96):

- Collection of concomitant medications (if applicable)
- Collection and monitoring of vital signs: blood pressure, temperature, heart rate, oxygen saturation
- Abbreviated physical exam
- Collection of blood for SOC hematology, coagulation, clinical chemistry, and biomarkers
- Document urine volume, urinalysis
- 12-Lead EKG
- AE review and reporting

Study Day 7 (Hour 168):

- Collection of concomitant medications (if applicable)
- Collection and monitoring of vital signs: blood pressure, temperature, heart rate, oxygen saturation

- Collection of blood for SOC hematology, coagulation, clinical chemistry, and biomarkers

Study Day 28

- Phone call or chart review to document morbidity and mortality

Study Day 90

- Surviving subjects will be asked to come for a close out visit. However, this population is notorious for compliance issues and if they do not come in a phone call and chart review will be done along with assessment via national death register

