1.2 SCHEMA

1.3 SCHEDULE OF ACTIVITIES (SOA)

| Assessments | Hour 0 | Q 24 hrs 1st 7 days or in ICU | Hour 48 | Hour 96 | Hour 168 | Day 28 | Day 90 |
|---|--------------------------|--|---------------------------|---------------------------|----------------------------|--------------------------|--------------------------|
| VS: BP, HR, MAP, RR, Temp., O2 sats, CVP, Glasgow Coma Scale, West-Haven Scale | S | | S | S | S | | |
| Body Weight | S | | S | S | | | |
| Suspected or known site of sepsis | S | | S | S | S | R | R |
| I/Os Total and Urine and urinalysis for crystalluria | S | R | R | R | | | |
| Assessment of Renal Function with serum creatinine, urine output and Use of Dialysis | S | | S | S | S | S | |
| Calculate MELD Score (most study by biostatistician) | S | | S | S | S | | |
| Labs: Arterial Blood Gases, Na+, K+, BUN, Cr, WBC, Hgb, Hct, Platelets, PT/INR | S | | S | S | S | | |
| Bilirubin Total, AST, ALT, ALP, albumin | S | | S | S | S | | |
| Need for Vasopressors or Inotropes: Epi, Nor-epi, Phenylephrine, Vasopressin, Dopamine | S | | S | S | S | | |
| All concomitant medications including: Methylprednisone, Hydrocortisone, N-acetylcysteine, Antibiotics, Thiamine, Albumin | S | | S | S | S | | |
| AE/SAE Assessments | R | | R | R | R | | |
| Blood for Biomarkers and TEG | R | | R | R | R | | |
| ICU Free Days | | | | | | R | |
| Hospital Free Days | | | | | | | R |
| Glucose Monitoring | S | S | S | S | S | | |
| EKG Monitoring | S | R | R | R | | | |
| All-Cause Mortality | | | | | | R | R |

S = Standard of Care
R = Research

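### Section 8.1 lists no urinalysis at hour 72, the schedule can be read as requiring one, and without it the crystalluria dose cut can hardly act after hour 48 (minor)

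*Combined protocol and SAP*

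**What the plan says.** Section 8.1 gives a task list for each treatment day. Under the heading that begins "Treatment Day 3 (Hour 72", the only urine item is "Document urine volume". At hours 24, 48 and 96 the item is "Document urine volume, urinalysis".

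The schedule of activities (section 1.3) has a single row, "I/Os Total and Urine and urinalysis for crystalluria". It is marked as standard of care at hour 0, and as research in the column headed "Q 24 hrs 1st 7 days or in ICU", at hour 48 and at hour 96. It is blank at hour 168. The row "EKG Monitoring" carries the same marks.

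The synopsis (section 1.1) sets the safety endpoints, QTc and crystalluria, at hours 24, 48 and 96. Section 3 gives the same three hours for safety documentation and explains the monitoring: "AscA can be excreted from kidney and lead to crystalluria, so will monitor urine pH via urinalysis".

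Section 7.1 sets the dose rule. If a subject, among other triggers, "develops crytalluria on urinalysis, or QTc prolongation >50% baseline, we will reduce the subsequent doses by 50" percent.

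**The concern.** The 7.1 rule is triggered by a urinalysis result, so it works only when a test is done while doses remain. Under 8.1 the interval between listed urinalyses is 24 hours up to hour 48 and then 48 hours, to hour 96. Dosing ends at about hour 96. Crystalluria that first appears in the second half of treatment would then be found when there is little or nothing left to reduce. If the schedule's every-24-hour mark covers urinalysis, an hour-72 test is already planned and 8.1 fails to list it. Staff working from 8.1 and staff working from the schedule could therefore apply different safeguards to the same patient.

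What is at stake is participant safety and the detection of crystalluria between hours 48 and 96, not the efficacy analysis.

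**Working it through.** **Texts side by side**

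| Hour | Section 8.1 urine item | Section 1.3 combined row | Synopsis safety time |
|---|---|---|---|
| 24 | volume and urinalysis | every-24-h mark (no hour-24 column) | yes |
| 48 | volume and urinalysis | marked | yes |
| 72 | volume only | every-24-h mark (no hour-72 column) | no |
| 96 | volume and urinalysis | marked | yes |
| 168 | no urine item | blank | no |

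**Inputs.** One dose every 6 hours, 16 in all (section 4.1). Dose 1 normally within 6 hours of randomization (6.1.2). Daily dose 200 mg/kg in four equal parts (4.1, 6.1.2). Reduction of later doses by 50% (7.1).

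**Assumptions.** Hour 0 is randomization, doses fall at their nominal times without the ±3-hour window, dose 1 is not delayed beyond hour 6, and the urinalysis result is available at the hour of the test.

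**Dose count.** 96 / 6 = 16, which agrees with the stated total.

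**Dose times.** Dose i is given at t0 + 6 × (i − 1), for i = 1 to 16.

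- Dose 1 at hour 0: doses at 0, 6, ..., 90. After hour 48: 54, 60, 66, 72, 78, 84, 90, which is 7. Still changeable at hour 72: 78, 84, 90, which is 3, or 4 if the hour-72 dose waits for the result. At or after hour 96: 0.
- Dose 1 at hour 6: doses at 6, 12, ..., 96. After hour 48: 54 to 96, which is 8. Still changeable at hour 72: 78, 84, 90, 96, which is 4, or 5 if the hour-72 dose waits. At hour 96: 1 if that dose waits for the result, otherwise 0.
- Dose 1 in between, for example at hour 3: doses at 3, 9, ..., 93. After hour 48: 51 to 93, which is 8. After hour 72: 75, 81, 87, 93, which is 4. After hour 96: 0.

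**Drug amount.** Each dose is 200 / 4 = 50 mg/kg, the course is 16 × 50 = 800 mg/kg, and halving withholds 25 mg/kg per dose.

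| Test read at | Doses that can be halved | Withheld (mg/kg) | Share of 800 mg/kg |
|---|---|---|---|
| Hour 72 | 3 | 3 × 25 = 75 | 9.4% |
| Hour 72 | 4 | 4 × 25 = 100 | 12.5% |
| Hour 72 | 5 | 5 × 25 = 125 | 15.6% |
| Hour 96 | 0 | 0 | 0% |
| Hour 96 | 1 | 1 × 25 = 25 | 3.1% |

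These are amounts withheld in a patient on vitamin C who has a positive result. They are not estimates of harm.

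**The case against.** The strongest reply is that 8.1 may be exactly what was intended. Its urinalysis hours are the synopsis and section 3 safety hours, so three sections share one pattern. The schedule row is composite and begins with intake and output, a natural daily item. Its every-24-hour column spans seven days, yet the row is blank at hour 168, so the mark cannot be applied literally to urinalysis over the whole span. Daily intake and output with urinalysis at 24, 48 and 96 is a coherent reading of all the texts.

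There is evidence the other way. The schedule has no hour-24 column, so the every-24-hour mark is the only place it can hold the hour-24 urinalysis that 8.1 requires. The EKG row has identical marks, and 8.1 does list an EKG at hour 72, although the synopsis gives QTc the same three hours; endpoint times therefore do not bound monitoring. But the EKG comparison cuts both ways, because at hour 72 the authors kept the EKG and left out the urinalysis. A reader might infer that the schedule plainly requires the test and that 8.1 is a slip. The documents do not support that certainty.

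A reader might also infer that patients would come to harm. That is not shown either. No crystalluria incidence is given. Section 2.2 reports steady-state ascorbate within 24 hours at this dose in the earlier sepsis trial, so the tests at hours 24 and 48 already sample steady exposure and first onset afterwards may be uncommon. Patients with kidney stones or with chronic kidney disease of stage IIIb or above are excluded. Urine volume, chemistry, examination and adverse event review continue at hour 72.

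What stands is narrower: for a patient whose crystalluria does begin after hour 48, the 8.1 list leaves the 7.1 rule almost nothing to act on. A urinalysis ordered for clinical reasons could close the gap. However, the schedule classes this test as research during treatment, so routine care should not be relied on to supply it.

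**Conclusion.** The point holds as a minor matter of safety monitoring and consistency. Sections 8.1 and 1.3 can be read differently at hour 72, and the documents do not settle which is meant. If 8.1 is followed and no other urinalysis is done, crystalluria first arising after hour 48 is not looked for until hour 96. At that point 0 doses remain, or at most 1, against 3 to 5 with an hour-72 test. The counts rest on nominal dose times, a first dose between hours 0 and 6, and an immediate result. The number of patients affected cannot be stated. The primary endpoint, power and alpha are unaffected.

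**What to change.** In section 8.1, at hour 72, change "Document urine volume" to "Document urine volume, urinalysis", as at hours 24, 48 and 96. In section 1.3, make clear that the every-24-hour mark for urinalysis applies through hour 96, for example by separating urinalysis from intake and output. The synopsis endpoint times may stay, since monitoring can be more frequent than endpoint reporting.

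The cost is at most 20 additional urinalyses (20 patients × 1 test), in a row that the schedule already marks as research. If no hour-72 test is in fact wanted, the schedule should say so and the plan should give a reason for the 48-hour interval.
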